Cover Page

Title: Brief Protocol Summary-- Addressing Intersectional Stigma: Testing THRIVE 365 for Black Sexual Minority Men (On The Daily)

NCT Number: NCT05376397

Document Date: 12/18/2023

Brief Protocol Summary

The sample consisted of Black sexual minority men (SMM) living with HIV and connected with the community-based organization, THRIVE SS. THRIVE SS is an Atlanta, GA based CBO that focuses on health equity for Black SMM, most of whom are living with HIV, through cultivating peer support, advocacy, and community building. The study team recruited a nonrandom purposive sample through advertisements on THRIVE SS's social media and email blasts. Eligibility criteria for this analysis were: 16 years old or older, identifying as masculine, identifying as Black/African American, reporting being attracted to and/or sexually active with men, able to complete all procedures in English, mobile access to the internet in order to complete the once-daily survey procedures. After the screening eligible for the study, participants received an invitation to participate in a HIPPA compliant WebEx informed consent meeting and baseline assessment with a trained research assistant. After baseline was a 14-day daily diary study with surveys administered on an Internet-based Qualtrics platform. Across all days, participants received 8 PM text-messages with links to their daily surveys. For those who had not completed the survey by 9:30 PM, they received an automatic reminder message. Surveys included measures of psychological and behavioral variables. We used simple randomization to vary the order of administration of all instruments. In line with a pre-post, one-arm trial, participants did not have access to the iTHRIVE 365 intervention for days 1–7 then received access to register and use the invention for days 8–14. The follow-up assessment occurred at the end of the 2-week daily diary period. We collected summary paradata (i.e., process data detailing app usage) on intervention page access. Participants received \$30 for baseline and follow-up and \$1.50 per survey for the first 7 daily surveys and \$2.50 for the next 7 surveys, with a \$5 bonus for completing all surveys (total maximum: \$93). The Rutgers University institutional review board approved all study procedures.

iTHRIVE 365 is a multicomponent intervention that uses mHealth features in alignment with 4 community priorities identified in our formative CBPR research: (1) Support HIV and psychological health knowledge and motivation; (2) Foster a sense of community and positive social connections among Black SMM; (3) Connect users to Black SMM-affirming health care, including HIV treatment and mental health care; (4) Provide resources for housing, transportation, and other economic empowerment. In line with best-practices for administering and testing interventions with mHealth components with trials of intervention principles (TIPs), iTHRIVE 365 deploys intervention elements that contain content that may be updated to maintain user engagement, but ultimately serve to accomplish delineated intervention strategies that match the community priorities. iTHRIVE 365 uses these intervention elements: (1) Weekly HIV and psychological health information and motivation content and daily health notifications; (2) Online moderated forums, interpersonal chats, and community calendars; (3) Linkage to biopsychosocial health care via THRIVE SS's network of Black SMM-affirming providers; and (4) Housing and economic resources through THRIVE SS's direct support and referral network. The health knowledge and motivation content includes a health maintenance notification system and content covering HIV and psychological health content that are evidence-based and culturally-tailored by the

Rutgers School of Public Health and THRIVE SS team for Black SMM. The health maintenance notification system allows users to input the timing and dosage of medications or health practices (e.g., mindfulness meditation) to receive personalized reminders. Similar notification systems, such as automated pill reminders, have been shown to improve ART adherence. The HIV health content includes educational and motivational material developed by THRIVE SS that is supported by evidence-based HIV treatment approaches. The psychological health content includes psychoeducation and exercises from cognitive behavioral therapy (CBT), positive psychology (PPI), and dialectic behavioral therapies (DBT) aimed at promoting individual education and motivation and facilitating users to identify and replace negative thought and behavioral patterns consistent with a transtheoretical approach. In the pilot version of iTHRIVE 365 tested here, the health knowledge and motivation content was housed in the home/landing and pill reminder pages. The social support content includes a community calendar that provides up-to-date information on THRIVE SS-led and other Black SMM community events in the Atlanta, GA area and gives users the option to receive reminder notifications about them. It also includes evidence-based features such as a moderated forum with discussions on topics generated by THRIVE SS staff or proposed by users and approved by staff. These forums have supported discussions on topics such as confronting stigma, medication side effects, and shared interests in popular culture. In line with guidance from formative focus groups, the forums are meant to support community around more than just HIV (e.g., finances, music) and include community guidelines that require users to refrain from personal attacks, hateful language, and other forms of communication that may cause forums to be unsafe for users. Forum moderators are THRIVE SS staff who identify violations of community guidelines. The interpersonal chat is a private chat between users that is only restricted if a user reports a violation of community guidelines. In the pilot version of iTHRIVE 365 tested here, the social support content was housed in the community, calendar, and chat pages. The access to affirming health care feature allows users to request THRIVE SS institutional support including linkage to psychotherapy, Black SMM support groups, HIV care, and COVID care. THRIVE SS draws on a network of Black SMM-affirming Atlanta, GA-area health care providers that has been developed and vetted by THRIVE SS over 10 years through site visits and qualitative evaluations from staff and members that assess aspects of affirming contexts (e.g., ease of access, patient comfort, and provider cultural humility). Given the timing of the deployment of this version of iTHRIVE 365 first in 2021, we included a CDC COVID screener (<https://www.cdc.gov/screening/index.html>) in this section. The housing and economic empowerment resources linkage features allow users to request free transportation, food assistance, culturally-appropriate clothes, and connection to housing support. Transportation costs are covered through paid transit passes and direct cash assistance. Clothes and food assistance are provided on-site at THRIVE SS and through THRIVE SS partner organizations. Housing assistance is managed by THRIVE SS case workers and includes transitional housing at a THRIVE SS-owned transitional home that provides housing for up to 5 months for those seeking a permanent residence and referrals to housing vouchers and other housing support in THRIVE SS's network. In the pilot version of iTHRIVE 365 tested here, the access to affirming health care and economic empowerment features were housed in the linkage page.

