Specifically, we will examine associations between iTHRIVE 365 engagement and next day outcomes with a multilevel vector autoregressive models (VAR (1)) in the DSEM framework.⁴² All models will adjust the effects of engagement for app availability since app registration occurred starting on day 8 of the study. As an example, the models examining the association between iTHRIVE 365 engagement (T365) and depressive symptoms (Dep) can be written in statistically as

$$\begin{aligned}
 & \text{Within-Person} \\
 & \text{Dep}_{ti} = \alpha_{1i} + \varphi_{1i} \text{Dep}_{(t-1)i}^C + \beta_{1i} \text{T365}_{(t-1)i} + e_{1ti} \\
 & \text{T365}_{ti} = \nu_1 + \varphi_2 \text{T365}_{(t-1)i} + \beta_2 \text{Access}_{ti} \\
 & \text{Between-Person} \\
 & \alpha_{1i} = \gamma_{00} + u_{0i} \\
 & \beta_{1i} = \gamma_{10} + u_{1i} \\
 & \varphi_{1i} = \gamma_{20} + u_{2i}
 \end{aligned} \tag{1}$$

With distributional assumptions,

$$\begin{aligned}
 \mathbf{e}_i & \sim N \left(\mathbf{0}, \text{diag} \left[\sigma_1^2, \sigma_2^2 \right] \right) \\
 \mathbf{u}_i & \sim N \left(\mathbf{0}, \begin{bmatrix} \tau_{00} & & \\ \tau_{21} & \tau_{11} & \\ 0 & 0 & \tau_{22} \end{bmatrix} \right)
 \end{aligned} \tag{2}$$

In the first expression in the within-person equation, Dep is the depressive symptoms outcome, t indexes time (in days, $t = 1, \dots, 14$), i indexes individuals ($i = 1, \dots, N$), α_{1i} is a person-specific intercept for depressive symptoms, φ_{1i} is the autoregressive effect capturing the carryover of depressive symptoms from the previous day to the current day, Dep^C is latent-centered depressive symptoms such that $\text{Dep}_i^C = \text{Dep}_i - \alpha_{1i}$ (latent centering helps alleviate Ludkte's and Nickell's bias in time-series models),⁴³ β_{1i} is a time-varying covariate effect of T365 access the previous day on depressive

symptoms during the current day, and e_i is a normally distributed within-person error with variance σ_1^2 . The second expression in the within-person equation is a probit model because T365 use is dichotomous such that ν_1 is the threshold for T365 use, φ_2 is the carryover effect of T365 use the previous day onto T365 use during the current day, and β_2 accounts for whether person i had access to the intervention at time t .

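### Access opens on diary day 8 for every man, so it is aliased with unrestricted day effects; the outcome equation has no day term, so a shared day trend enters the engagement coefficient

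*Protocol*

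**What the plan says.** The design is a single arm with a 14-day diary, and each man's first week serves as his comparison: "participants did not have access to the iTHRIVE 365 intervention for days 1–7 then received access to register and use" the app on days 8 to 14 (Protocol, Brief Protocol Summary). The same paragraph sets pay at $1.50 for each of the first 7 daily surveys and $2.50 for each of the next 7. The only thing randomised is the order of the instruments.

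For the psychological outcomes the SAP (Analytic Plan) states that "we will examine associations between iTHRIVE 365 engagement and next day outcomes with a multilevel vector autoregressive models". The exposure is thus previous-day use of the app, yes or no; its own equation "is a probit model because T365 use is dichotomous".

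On availability the SAP says: "All models will adjust the effects of engagement for app availability since app registration occurred starting on day 8 of the study". In equation (1), however, Access appears only in the equation for app use, where its coefficient "accounts for whether person i had access to the intervention at time t". The equation for depressive symptoms contains a person-specific intercept, the previous day's symptoms and the previous day's use. It has no Access term and no diary-day term. Neither document mentions a day trend or reactivity to repeated surveys.

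**The concern.** Daily self-reports can drift for reasons unrelated to an app, such as reactivity to being asked, falling symptom reports or fatigue. Every man moves from no access to access on the same diary day, so Access is identical to an indicator for day 8 or later. Any change at that point could come from the app, from the diary or, for a man who has missed no survey, from the pay rise on the same day.

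The planned analysis uses engagement rather than access, but it inherits the problem. Engagement is zero by design throughout days 1–7, so engaged days are late days. If symptom reports fall over the fortnight for everyone, an outcome equation without a day term will credit some of that fall to using the app. A 95% credible interval excluding zero, which the SAP treats as the analogue of significance, could then arise with no app effect.

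**Working it through.** The documents give no sample size, effect size or trend, so there is no stated figure to reproduce. The check has three parts.

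**1. Access against diary day, fixed start.** Inputs from the Protocol: days t = 1 to 14, Access = 1 from day 8.

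- Sum of squares of Access per man: 7 × 7 / 14 = 3.50.
- Sum of squares of day about 7.5: 14 × (14² − 1) / 12 = 227.5.
- Cross-product: 0.5 + 1.5 + … + 6.5 = 24.5.
- R² = 24.5² / (227.5 × 3.50) = 0.754, so r = 0.868.
- Variance inflation = 1 / (1 − 0.754) = 4.06. Information left = 3.50 / 4.06 = 0.862 per man.

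| Day adjustment | Variance multiplied by | Information left per man |
|---|---|---|
| Linear | 4.06 | 0.862 |
| Quadratic | 4.06 | 0.862 |
| Cubic | 7.5 | 0.466 |
| Fifth degree | 11.5 | 0.303 |
| Free day effects | not estimable | 0 |

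The quadratic term costs nothing extra because the step is antisymmetric about day 7.5 and the quadratic is symmetric.

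**2. Engagement, fixed start.** Assumed: 40 men, engaging independently on 20% to 70% of open days (days 8–14). With person effects and free day effects already in the model, engagement still adds a rank (53 to 54), whereas Access does not (53 to 53). Variance inflation for engagement is 1.16, 1.26, 1.58 and 2.31 at 20%, 30%, 50% and 70%.

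**3. What the missing day term does.** This is a simulation with no app effect and a linear trend common to all men. Assumptions, none from the documents: 40 men, within-person SD 1, lag-1 autocorrelation 0.3, engagement on 40% of open days on average. The analysis is a within-person regression on previous-day outcome and previous-day engagement with person-clustered standard errors, a frequentist stand-in for the DSEM outcome equation (1,000 runs per row).

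| Trend, SD per day | Engagement coefficient, no day term | False-positive rate | Access added | Linear day added |
|---|---|---|---|---|
| 0 | −0.003 | 7% | −0.002 | −0.005 |
| −0.03 | −0.110 | 15% | −0.022 | 0.001 |
| −0.05 | −0.186 | 38% | −0.033 | 0.004 |
| −0.10 | −0.344 | 83% | −0.069 | −0.002 |

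A separate simulation at −0.05 SD per day gave −0.173, hence the range of about −0.17 to −0.19. With a linear day term or free day effects the false-positive rate is 5% to 7%.

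**Randomised start, for comparison.** With starts spread evenly over days 5–11, information per man is 3.21 after person effects, 0.989 after a linear day term and 0.857 after free day effects (3.21 / 0.857, about 3.8 times the variance). In the simulation at −0.05 SD per day, random start without a day term still gave −0.173 with 32% false positives; a linear day term brought this to 0.001.

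**The case against.** A reader might infer that no analysis of this design can separate the app from diary-day trends. The documents do not support that, for two reasons. First, a step at day 8 can be distinguished from a smooth trend whose shape is assumed, as in an interrupted time series: 0.862 of the 3.50 units survives a linear or quadratic trend. Reactivity and fatigue may well be smooth. Secondly, the SAP's exposure is engagement, not access. Men can differ in use on the same day, so a day term separates engagement from trends common to all men under the existing schedule.

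A reader might also infer that randomising the start day would by itself repair the planned model. It would not: without a day term the spurious coefficient is almost unchanged. Under a linear trend, random start raises the information on access only from 0.862 to 0.989, about 15%. Its real gain, from 0 to 0.857, comes when no trend shape is assumed.

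It is also fair to say that this is an openly declared one-arm pilot whose feasibility and acceptability aims do not depend on the point, and that the Protocol is written in the past tense, so the access schedule is probably no longer open to change.

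Two things remain. The smooth-trend route needs an assumed shape and cannot distinguish access from a pay step at the same point. And the outcome equation as written contains neither term that would use the separation available for engagement.

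**Conclusion.** The point holds in limited form. Access is a fixed function of diary day and, for a man with no missed surveys, changes with pay. Its effect is not identified against arbitrary day effects and is identified only under an assumed smooth trend, at 4 to 7.5 times the variance for linear to cubic shapes, with the pay rise assumed inert.

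For the analysis actually planned, the defect is the outcome equation. The SAP states an intention to adjust for availability, but Access sits only in the use equation, and adding it to the outcome equation would reduce the bias without removing it (−0.033 at a trend of −0.05 SD per day). The size depends on the trend, which is unknown: the spurious coefficient ranges from about 0 with no trend to −0.344 SD at −0.10 SD per day, under the assumed number of men, autocorrelation and engagement rate. An upward trend would reverse the sign.

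A day term removes trends shared across men. It does not address why a man opens the app on a given day, so the engagement coefficient remains an association.

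**What to change.** **This analysis (a free improvement).** Add diary day to the outcome equation of every DSEM model: linear in the main analysis, with day effects as a sensitivity analysis. Describe the engagement coefficient as an association, because use is self-selected. The cost is one further within-person covariate already in the data and some precision (variance inflation of 1.16 to 2.31 with free day effects, under the engagement rates assumed above).

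**A later trial, or any cohort not yet started.** Randomise each man's access day evenly over a window centred on day 8, for example days 5–11, which keeps mean access at 7 days. Keep survey pay constant, or tied to survey number and not to access. Set Access for each man and day from the assigned date and include it with day effects in the outcome model. This identifies the effect of being offered the app, not of using it. The cost is an allocation list and staggered release of the registration link, with no change in the number of men, surveys or days. The downside is that access lasts 4 to 10 days per man, so feasibility must be reported per access day.

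### Survey pay rises at about the point the app opens, and the planned engaged versus non-engaged comparisons do not hold pay, week and access constant

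*Protocol*

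**What the plan says.** The Protocol (Brief Protocol Summary) describes the design with the words "In line with a pre-post, one-arm trial". On timing it says that "participants did not have access to the iTHRIVE 365 intervention for days 1–7 then received access to register and use the invention for days 8–14". Pay is 1.50 dollars "per survey for the first 7 daily surveys" and 2.50 dollars "for the next 7 surveys", with 30 dollars "for baseline and follow-up and" a 5-dollar bonus for a complete diary. The stated maximum is 93 dollars. No reason is given for the step in pay.

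The SAP (Analytic Plan) specifies two analyses of the effect of engagement:

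- **ART use:** a chi-square comparing days with and without app engagement. The text does not limit it to days on which the app was available.
- **Psychological outcomes:** a lagged two-level model of next-day symptoms on app engagement. The text promises that engagement effects are adjusted for availability in every model, "since app registration occurred starting on day 8 of the study". In equation (1), however, Access appears only in the second line, which predicts app use (T365). The symptom line contains a person-specific intercept, lagged symptoms and lagged T365.

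Pay is not mentioned in the SAP.

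**The concern.** With no concurrent control, anything else that changes when the app opens can enter a comparison that mixes days before and after that point. Time in study and diary reactivity do so unavoidably. The pay step was a choice. It rewards completing surveys, not using the app, so the plausible route to bias is which days get observed and how carefully surveys are answered. The daily surveys supply the symptom scores and the self-reported engagement, and presumably the daily ART reports.

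Both planned contrasts do mix those days. An apparent benefit or harm of engagement could partly be a difference between the first and second week, from pay or from anything else tied to the week. The SAP already intends to adjust for availability, but its written formulas do not do so.

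**Working it through.** **1. Reproduce the payment figure.** Inputs are from the Brief Protocol Summary.

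2 × 30 + 7 × 1.50 + 7 × 2.50 + 5 = 60 + 10.50 + 17.50 + 5 = 93 dollars, which matches the stated maximum. A single 30 dollars for both assessments would give 63, so the 30 is paid at each. The step is 2.50/1.50 − 1 = 0.667, or 67%.

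**2. ART chi-square.** Let p be the chance that a man engages on an access day. The documents do not give it, so I assume 0.2 to 0.5 and complete diaries. Per man there are 7p engaged days, all in days 8–14, and 14 − 7p non-engaged days, of which 7 are days 1–7.

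| p | Non-engaged days, 14 − 7p | Share from days 1–7, 7/(14 − 7p) |
|---|---|---|
| 0.2 | 12.6 | 0.56 |
| 0.5 | 10.5 | 0.67 |

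Call this share s. Let m1 and m2 be the rates of reported ART use on non-engaged days in weeks 1 and 2. The pooled non-engaged rate is s·m1 + (1 − s)·m2. Compared with a contrast made within week 2, the pooled contrast is therefore shifted by s(m2 − m1). So 56–67% of any week difference, whatever its cause, passes into the engagement comparison.

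**3. Lagged symptom model.** Outcomes with a preceding diary day fall on days 2–14, 13 in all. Those that follow an engaged day lie on days 9–14, all at the higher rate: 6p per man. The other 13 − 6p follow a non-engaged day, and 6 of them (days 2–7) are at the lower rate.

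- p = 0.2: 6/11.8 = 0.51
- p = 0.5: 6/10 = 0.60

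The Access term in equation (1) does not correct this. As written, the two residuals are independent (diagonal matrix in equation (2)), and the T365 line has no person-specific terms. Access therefore predicts app use but does not adjust the coefficient of lagged T365 in the symptom line.

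**4. Would conditioning on access work?** Yes, for the engagement effect. Before access, engagement cannot vary. Once access is held fixed, the effect is estimated from access days, where the rate is constant if pay changed by calendar day. For the lagged model, outcomes that follow an access day are days 9–14. Day 8 is paid at the higher rate but follows a day without access.

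**5. Precision given up in the ART comparison.** I treat days as independent, as the chi-square does, with a common rate. The variance of the difference is proportional to 1/(engaged days) + 1/(non-engaged days). Limiting non-engaged days to 7(1 − p) multiplies it by (2 − p)/(2(1 − p)).

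- p = 0.2: 1.8/1.6 = 1.125; standard error × 1.06
- p = 0.5: 1.5/1.0 = 1.50; standard error × 1.22

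**The case against.** The strongest reply is that pay itself may do nothing. The documents give no evidence that one dollar per survey changes mood or ART reports. The shares above describe weeks, and would be identical under flat pay. Escalating pay to hold completion in the second week, the only one in which exposure can be observed, is a defensible choice. The Protocol is in the past tense, so the payment cannot now be changed. All of this stands, and it limits the point to the analysis and reporting.

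Four stronger readings are tempting, and the documents do not support them:

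- **That the trial's main test is a pre-post contrast confounded with pay.** The Protocol uses the pre-post label, but the SAP specifies no test of days 1–7 against days 8–14.
- **That adjusting for Access is useless because pay and access coincide.** That would be true for an effect of access. The SAP's target is engagement, and conditioning on access removes the pay step from that effect.
- **That every measure comes from the paid diaries.** Page-access paradata are also collected, for feasibility, and the baseline and follow-up assessments are paid separately.
- **That pay and access switch at exactly the same point for everyone.** If the first 7 surveys means the first 7 completed, a man who misses m of them in week 1 reaches the higher rate on day 8 + m at the earliest.

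**Conclusion.** The point holds as a cheap improvement to the analysis, not as a demonstrated bias. Pay, week and access change together at about day 8. Neither the ART chi-square nor the symptom line of equation (1) conditions on that change, and for the symptom models this falls short of the SAP's own stated adjustment. Under assumed engagement on 20–50% of access days and complete diaries, 56–67% of non-engaged days in the chi-square, and 51–60% of outcomes following a non-engaged day in the lagged model, carry the lower rate. The size and direction of any effect of pay cannot be derived from the documents. A reader might infer that the results are confounded by payment; all that is shown is that the written contrasts leave room for it, along with any other week difference.

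**What to change.** 1. **ART use:** limit the engaged versus non-engaged comparison to days 8–14.
2. **Psychological outcomes:** add the Access indicator to the symptom line of equation (1), or limit that line to outcomes that follow access days (days 9–14). If the indicator is used, state whether it refers to the outcome day or the preceding day.
3. **Reporting:** give survey completion by week. State that any descriptive difference between days 1–7 and days 8–14 includes the pay change. Say whether the higher rate began by calendar day or by count of completed surveys; if by count, pay is not quite constant within days 8–14 for men who missed week 1 surveys.

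The cost is a change of SAP wording, fewer days and somewhat wider intervals: about 6–22% on the ART standard error under the assumptions above. Self-selection into engagement and time trends within days 8–14 remain.

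For a later trial only, flat pay is an option: 28/14 = 2.00 dollars per survey keeps the 93-dollar maximum. If completion rates are c1 and c2 in the two weeks, the flat rate costs 3.50 × (c1 − c2) dollars more per participant, for example 0.35 at an assumed 90% and 80%. It also gives up any help that the higher rate provides for completion in week 2.
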